7. SAMPLE SIZE JUSTIFICATION

The sample size is 26 in each of the 2 cohorts (Trained Users and Untrained Users). It is assumed that the percentages of successful dosing of NG and GEK will be 90% and 50%, respectively.

Additionally, a proportion of discordant pairs of 45% is assumed, which reflects a moderate within-subject correlation between the 2 treatments.

These numbers are based on the Yale 2017 study³, where 15 out of 16 (93.8%) NG simulations were completely successful and 8/16 (50%) GEK administrations were partially or completely successful in the “caregivers” group (the equivalent of the Trained Users group in this study). Note that for GEK, the “partial or complete success” rate is used. In Yale 2017, only 2 out of 16 (12.5%) simulations were completely successful for the GEK treatment. Hence, we are using a best-case scenario approach for the successful administration rates of GEK in the current study. In conclusion, the 90% success rate for NG is based on the Yale 2017 NG success rate (15/16, 93.8%, rounded down) and the 50% success rate for GEK is based on the best-case scenario from the Yale 2017 study, i.e. partial administration of GEK in 8/16 (50%) simulations.

Based on these numbers, the sample size will provide 90% statistical power to detect a statistically significant difference between success rates of NG and GEK, using the test with a 2-sided alpha level of 0.05.

Enrollment will be continued per group until 26 Trained Users have been recruited (stratified into 13 who have an accompanying PWD with T1DM, and 13 who have a PWD with T2DM) and 26 Untrained Users have been recruited.

Participants who are randomized but do not participate in the study simulations may be replaced to ensure that enough participants may complete the study.

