9.5 Statistical Methodology

The following endpoints will be summarized by treatment using descriptive statistics and listed:

- The percentage of Trained Users and Untrained Users that perform a successful administration
- The time taken by Trained Users and Untrained Users to successfully administer NG or GEK
- The percentages of Trained Users and Untrained Users who complete all of the critical steps
- The percentage of all simulations that result in a successful administration of NG, for all users combined
- The average length of time taken by PWDs to teach the use of NG and GEK to their associated Trained User,

The McNemar test will be used to assess the percentage of Trained Users that perform a successful administration. The exact-sign test will be used as a sensitivity analysis.

Successful administration will be assessed, for each cohort:

- NG (Trained User) versus GEK (Trained User)
- NG (Untrained User) versus GEK (Untrained User)

Example SAS code for the McNemar test

```
proc freq data = success;
  weight count / zeros;
  tables NG_trained*GEK_trained / agree;
  exact mcnem;
run;
```

Example SAS code for the exact-sign test

```
proc univariate data=success;
  var success_diff;
run;
```

Where `success_diff` is 1 if NG is successful and GEK is not, 0 if both treatments are successful or not successful and -1 if NG is not successful and GEK is successful.

For Part A (Trained Users), assessment of successful administration will also be stratified between those users who have an accompanying PWD with T1DM, and those who have an accompanying PWD with T2DM.

Time to administer a dose will be assessed using summary statistics, making the following comparisons:

- NG (Trained User) versus NG (Untrained User) – two sample t-test
- GEK (Trained User) versus GEK (Untrained User) – two sample t-test

- NG (Trained User) versus GEK (Trained User) – Paired t-test
- NG (Untrained User) versus GEK (Untrained User) – Paired t-test

This analysis, using descriptive statistics and the appropriate t-test, will be assessed for successful and unsuccessful administration combined, as well as successful administration only. Time needed to complete glucagon administration will be shown categorically based on the following categories:

- <30 seconds
- 30 seconds-45 seconds
- 45 seconds-1 minute
- 1 minute-1 minute 15 seconds
- 1 minute 15 seconds-1 minute 30 seconds
- 1 minute 30 seconds-1 minute 45 seconds
- 1 minute 45 seconds-2 minutes

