- 2 minutes-2 minutes 15 seconds
- 2 minute 15 seconds-2 minutes 30 seconds
- 2minutes 30 seconds-2 minutes 45 seconds
- 2 minutes 45 seconds-3 minutes
- 3-4 minutes
- 4-5 minutes
- 5-10 minutes
- >10 minutes

A graphical presentation of the successful administration times will be provided using a Kaplan-Meier plot.

To simultaneously model the training effect (Trained Users versus Untrained Users) and the treatment effect (NG versus GEK), a generalized estimating equations (GEEs) model will be performed, with treatment, training and the treatment-by-training interaction effect as independent variables, and the participant as participant identifier. As each Trained User and Untrained User will perform both the NG and the GEK administration, the data are paired for the device type but not paired for the level of training. Using a GEE model will enable estimation of both effects simultaneously, and also estimation of the interaction effect, which will test whether the difference between devices varies between Trained Users and Untrained Users. Furthermore, the randomization order (NG-GEK versus GEK-NG) can be tested within this model. Given the low sample size of this study and multitude of variables that can be entered, this GEE modelling will be exploratory in nature.

Primarily, a GEE model using the binary distribution (success versus no success) and the identity link will be produced: this will produce estimated rate differences with 95% confidence intervals. In case this model fails to converge, log or logit links can be attempted, to estimate relative risks or odds ratios, respectively.

Example SAS code:

```
proc genmod data=xx descending;
class subjid arm trt ftrt ;
model success = arm|trt ftrt / link=identity dist=bin;
repeated subject=subjid;
lsmeans arm*trt / ilink diff;
lsmeans arm / ilink diff;
lsmeans trt / ilink diff;
lsmeans ftrt / ilink diff;
run;
```

where arm = trained or untrained, trt = NG or IM and ftrt = first treatment received

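### The only stated 95% interval for the NG minus GEK success difference comes from a fragile exploratory GEE; a paired interval should stand beside the McNemar test

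*SAP*

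**What the plan says.** SAP 9.5 tests success in each cohort with McNemar and uses the exact-sign test as sensitivity analysis. The McNemar code, "tables NG_trained*GEK_trained / agree" plus a request for the exact test, asks for no interval for the rate difference.

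The interval appears later, in the GEE paragraph. The identity-link model is the first choice, and "this will produce estimated rate differences with 95% confidence intervals". Protocol 10.3 says the same. The SAP adds that "this GEE modelling will be exploratory in nature"; the protocol says only that it can be.

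The text and the code describe different models. The text specifies a model "with treatment, training and the treatment-by-training interaction effect as independent variables" and treats order as an option: "Furthermore, the randomization order (NG-GEK versus GEK-NG) can be tested within this model". The only model statement given is "model success = arm|trt ftrt / link=identity dist=bin", where `ftrt` is the first treatment received.

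The fallback reads: "In case this model fails to converge, log or logit links can be attempted, to estimate relative risks or odds ratios, respectively".

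SAP 7 plans on 90% success for NG and 50% for GEK. It calls the GEK figure a best case, because it counts partial successes in the cited earlier study, where "only 2 out of 16 (12.5%) simulations were completely successful for the GEK treatment".

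**The concern.** The rate difference is the natural summary of the primary (Trained User) and first secondary (Untrained User) comparisons. Its only stated interval depends on a model in which fitted probabilities are linear in the covariates and must stay between 0 and 1. With NG success expected near 90% and 13 participants per sequence, an extra additive term can push a fitted NG rate to 1. If the software then reports failure, the plan changes effect measure. At the planning rates the same result would read as 40 points, a relative risk of 0.90/0.50 = 1.8, or an odds ratio of (0.90/0.10)/(0.50/0.50) = 9.0. If it does not report failure, the standard error may be unreliable.

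The model without `ftrt` avoids most of this, but its interval is a paired Wald interval at n = 26, and the endpoint (all critical steps plus a complete dose) may give GEK success well below 50%.

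**Working it through.** **Inputs.** SAP 7: n = 26 per cohort, NG 90%, GEK 50%, 45% discordant, two-sided 0.05. Sensitivity rates, also from SAP 7: NG 15/16, GEK 2/16. Assumptions: complete pairs, 13 per sequence (Protocol 7.2 gives two schedules but no ratio), no true order effect, and the same rates in both cohorts.

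**Joint probabilities.** NG only: (0.45 + 0.40)/2 = 0.425. GEK only: (0.45 − 0.40)/2 = 0.025. Both: 0.90 − 0.425 = 0.475. Neither: 0.075.

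**The plan's own figure.** Enumerating all paired tables at n = 26 gives 90.8% power for the exact McNemar test. The stated 90% is reproduced.

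**With `ftrt`.** The REPEATED statement names no correlation type, so working independence applies. There are 8 cells (cohort × device × sequence) of 13. A fitted probability can reach 0 or 1 only in a cell that is all failures or all successes. One NG cell is 13/13 with probability 0.9^13 = 0.254, and at least one of the four with probability 1 − (1 − 0.254)^4 ≈ 0.69, so the condition is common. Maximising the likelihood under the 0–1 constraint shows how often the solution lies on the boundary:

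- Plan's rates: 54.1% of 6,000 simulated trials (smaller repeat runs: 51% to 56%). Of all trials, 12.0% have a 0% or 100% device-by-cohort cell; the other 42.1% are due to `ftrt`.
- NG 80%, GEK 50%: about 12–13%. NG 95%, GEK 50%: 83–85%.
- Cited rates in both cohorts: 79.7% of 4,000 (repeat runs 77–78%).
- Untrained Users at 70%/30%, Trained Users at the plan's rates: 37%.

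**Without `ftrt`.** The model is saturated, so only a 0% or 100% device-by-cohort cell puts it on the boundary. NG 26/26 has probability 0.9^26 = 6.5% in one cohort and 1 − (1 − 0.065)² = 12.5% in either.

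**In one package (statsmodels, not SAS).** On the same 400 trials, 238 fits with `ftrt` did not converge; all 400 without it did. Convergence was not always reassuring: for NG 26/26 and GEK 14/26 it returned a standard error of 0.802, against 0.098 from the paired formula.

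**Interval without `ftrt`.** Let b and c be the numbers succeeding only with NG and only with GEK, and d = (b − c)/n. Away from extreme cells the robust standard error equals the paired Wald value √{[(b + c)/n − d²]/n}. Coverage by full enumeration at n = 26 (Newcombe with continuity-corrected phi):

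| Rates | Wald | Newcombe | Tango |
|---|---|---|---|
| 90% / 50%, 45% discordant | 93.5% | 95.7% | 94.7% |
| 15/16 and 2/16, independent | 86.9% | 94.7% | 96.5% |
| 15/16 and 2/16, maximum correlation | 87.5% | 95.4% | not computed |

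At the cited rates the Wald upper limit exceeds 100 points in 28.2% of trials (independent) or 25.0% (maximum correlation); Newcombe's never does.

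**What drives the shortfall.** At GEK 50% and 50% discordant, Wald coverage is 92.9%, 93.5%, 94.5% and 92.6% at NG 92%, 95%, 98% and 99%: no trend. Averaged over GEK 40–60% it is 93.3–93.4% for NG anywhere from 80% to 99.5%. With GEK 10–20% and NG 90–98% under independence, it lies mostly between 82% and 93%, with isolated points up to 94%: for example 92.9% at 90%/12.5%, 89.8% at 95%/15%, 82.3% at 98%/10%.

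**Worked case.** NG 24/26, GEK 0/26: b = 24, c = 0, d = 0.923. SE = √[(0.9231 − 0.8521)/26] = 0.0523. Wald: 0.923 ± 1.96 × 0.0523 = 82.1 to 102.6 points. Newcombe uses the Wilson limits 0.759–0.979 for NG and 0–0.129 for GEK, with phi = 0. Lower: 0.923 − √(0.164² + 0.129²) = 0.714. Upper: 0.979. That is 71.4 to 97.9 points.

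**The case against.** The primary and first secondary objectives are hypothesis tests, and nothing here touches them. The GEE is declared exploratory, its code is labelled an example, the text-defined model omits `ftrt`, and convergence failure is foreseen. All of that stands, and it limits the weight of the point.

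Three stronger readings are tempting but unsupported. First, a reader might infer that the interval will be missing in half of trials. A boundary solution is a property of the likelihood; SAS GENMOD was not run and may fail, or may report convergence. The one-half figure also rests on equal rates in both cohorts and a 13/13 split. Second, a reader might infer that high NG success alone makes the Wald interval too narrow. It does not; the material shortfall needs low GEK success and hence a large difference. Even there 86.9% is a low point on a discrete curve, and 2/16 comes from a small group. Third, a reader might infer that no other interval is planned anywhere. SAP 3 places detailed outputs in TFL shells that are not available, and the exact-sign code analyses the paired difference itself, so its software output may include a standard error. Neither document names such an interval.

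**Conclusion.** The point holds as a reporting weakness that should be corrected. Within the protocol and SAP, the precision of the device difference is tied to an exploratory model whose code conflicts with its text. With `ftrt`, about half of trials at the plan's rates have no interior fit, under the assumptions listed; across the scenarios tried, the share runs from about 12% (NG 80%) to about 85% (NG 95%). Without `ftrt`, the boundary problem falls to 12.5% of trials for either cohort at the plan's rates. The resulting Wald interval is only slightly narrow near the planning rates, but it under-covers materially if GEK success is as low as the cited complete-success rate. How SAS would behave in boundary trials is unknown.

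The McNemar p-values, the two success percentages and the 90% power stand.

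**What to change.** 1. In SAP 9.5, pre-specify for each cohort the paired NG minus GEK success-rate difference with a 95% interval from the 2×2 table, reported next to the McNemar p-value whatever the GEE does. Use Newcombe's paired method and state that phi is continuity-corrected: the uncorrected version covers 95.1% at the plan's rates and 93.1% at the cited rates, against 95.7% and 94.7%. Tango's score interval is an acceptable alternative.
2. Fit the exploratory identity-link GEE with `arm`, `trt` and their interaction only, as the text defines it. Remove `ftrt` from the class, model and lsmeans lines. Test order separately, for example by an exact test within cohort comparing each participant's number of successes (0, 1 or 2) between sequences.
3. Do not rely on naming a single fallback link. Once `ftrt` is removed, the remaining boundary cases are 0% or 100% cells, where log and logit links also lack a finite estimate for some effects. The paired interval keeps the rate-difference scale.

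The cost is a few lines of SAP text and code, with no new data and no change in conduct. The mean interval width rises from 40.4 to 41.9 points at the plan's rates, and from 30.1 to 33.4 points at the cited rates under independence.

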9.6 Other Assessments

All other assessments not detailed in previous sections will be listed but not summarized or statistically analyzed.

10. INTERIM ANALYSES

No interim statistical analyses are planned.

11. CHANGES FROM THE PROTOCOL SPECIFIED STATISTICAL ANALYSES

There were no changes from the protocol specified statistical analyses.

13. DATA PRESENTATION

13.1 Derived Parameters

N and percentage values should be reported as whole numbers. Median values should be treated as an observed parameter and reported to the same number of decimal places as minimum and maximum values.

13.2 Missing Data

Missing data will not be displayed in listings.

13.3 Insufficient Data for Presentation

Some of the TFLs may not have sufficient numbers of subjects or data for presentation. If this occurs, the blank TFL shell will be presented with a message printed in the center of the table, such as, "No serious adverse events occurred for this study."
